3.3 Lifestyle Modifications

All participants must agree to the following lifestyle modifications at enrollment and throughout the duration of the study. Participants are eligible to enroll in the study if they:

- Are willing to commit to medication dosing, therapy sessions, follow-up sessions, completing evaluation instruments, and all necessary telephone contact.
- Agree to not participate in any other interventional clinical trials during the duration of this study without prior approval of the Medical Monitor.

Leading up to Experimental Sessions

- Agree to take nothing by mouth except alcohol-free liquids after 12:00 A.M. (midnight) the evening before each Experimental Session.
- Refrain from the use of any psychoactive medication not approved by the research team from Baseline through Study Termination.
- Agree not to use caffeine or nicotine for 2 hours before and at least 6 hours after the initial dose during each Experimental Session.
- Agree not to use alcohol or cannabis after 12:00 A.M. (midnight) before each Experimental Session.
- Are willing to comply with medication requirements per protocol (refer to Section 11.0 Concomitant Medications). Medications will only be discontinued after enrollment per clinical judgment of the site physician in consultation with the prescribing physician.
- Are able to decrease dose of allowable opioids (per Section 11.0 Concomitant Medications), if used for pain management, leading up to the Experimental Session in order to avoid taking the medication for at least 12 hours prior to the initial IMP administration and 24 hours after. During this period, the participant will be allowed to take the medication if needed for intolerable pain flare-ups or to prevent withdrawal symptoms.
- Agree that, for 1 week preceding each Experimental Session to refrain from:
 - o Taking any herbal supplement (except with prior approval of the research team).
- Agree that, for 5 half-lives of the medication preceding each Experimental Session they will refrain from:
 - Taking any nonprescription medications (with the exception of non-steroidal antiinflammatory medications or acetaminophen) unless with prior approval of the research team.
 - o Taking any prescription medications (with the exception of contraception, thyroid hormones, anti-hypertensives, or other medications approved by the research team).

Post Experimental Session (for exceptions, see Appendix A)

- Are willing to remain overnight at the study site after each Experimental Session until after the Integrative Session the next morning.
- Agree to not drive after each Experimental Session until after the Integrative Session the next morning.

4.0 Protocol Design

4.1 Study Design Overview

This multi-site open-label safety extension study of MDMA-assisted therapy for the treatment of participants with posttraumatic stress disorder will be conducted in $N\approx100$ participants, by invitation only.

For each participant, the study will consist of:

- **Screening Period**: phone screen, informed consent, eligibility assessment, and enrollment of eligible participants
- **Preparatory Period**: medication tapering, Preparatory Sessions
- **Treatment Period**: three monthly Experimental Sessions over up to 4 months, followed by Integrative Sessions
- Study Termination: Primary Outcome PCL-5 4 weeks after third Experimental Session
- Invitation to participate in Long-term Follow-up (LTFU) extension study: at least 6 months after last Experimental Session

The treatment consists of a flexible dose of MDMA, followed by a supplemental dose unless tolerability issues emerge, administered with therapy in three open-label approximately monthly Experimental Sessions. This Treatment Period is preceded by three Preparatory Sessions. During the Treatment Period, each Experimental Session is followed by three Integrative Sessions of non-drug therapy. Experimental Sessions are followed by an overnight stay; a sub-study (Appendix A) will assess feasibility of Experimental Sessions without an overnight stay. The Primary Outcome measure, the change in PCL-5 from Visit 3, is assessed at Visit 16.

Figure 1: Study Structure Overview

[figure not shown]

Table 1: Study Design Overview

	Screening Period From Consent to Enrollment (Visit 0): 1 to 10 weeks					
Study Visit		Visit Duration/ Visit Timing	Brief Description of Events			
Screening	Screening	Multiple visits over 7 to 70 days/ After phone screen	At initial visit, obtain Informed Consent and assess all screening measures (including PCL-5 and Interim C-SSRS), interim medical history, and interim and current medications. Contact outside providers and order medical records (as needed), physical exam, labs (including pregnancy and drug tests), ECG, and 1-minute rhythm strip. Once all results are obtained, review along with notes from all screening visits and measures. If eligible, send results of LEC-5 & C-SSRS to IR.			
	Independent Rater Screening	1 hour/ After initial screening visit	After initial eligibility is reviewed, an IR will conduct the MINI and C-SSRS via telemedicine. Results will be confirmed by clinical observation during the Preparatory Period, but the MINI will not be repeated.			
Enrollment	Enrollment (Visit 0)	1.5 hours/ 2 to 14 days after Independent Rater Screening	Prior to enrolling: review all screening measures, medical history, discussion with outside providers and sponsor, and any clarification phone calls with participant. Visit is 1.5 hours to review eligibility and medical tapering plan. If enrolled, begin taper, followed by five half-lives of drug or active metabolite (whichever is longer), (for stabilization prior to V3). For non-selective irreversible MAOIs, a 2-week washout period following the taper is required (3 weeks in the case of imipramine and clomipramine, tricyclic antidepressants with MAOI activity).			

Prep	Preparatory Period						
Fron	From Preparatory Session 1 (Visit 1) to Preparatory Session 3 (Visit 3): 1 to 11 weeks						
Stud	Study Visit/ Visit Duration/ Brief Description of Events						
Visit	:#	Visit Timing					
	Preparatory	1.5 hours/	90-minute Preparatory Session. Target visit timing on tapering				
	Session 1	0 to 14 days after	needs. If needed, schedule calls between Visits 1 and 2 if				
	(Visit 1)	Enrollment (V0)	indicated for tapering, safety, or further questions about				
			medical history or eligibility.				
	Preparatory	1.5 hours/	90-minute Preparatory Session. If tapering is complete or not				
-	Session 2	2 to 75 days after V1	needed, check eligibility and schedule Visits 3 and 4. If				
1.00	(Visit 2)		tapering is ongoing, schedule post taper call for ongoing				
Pel			assessment.				
Preparatory Period	Phone Call	1 hour/	If needed, confirm medication taper and stabilization is				
atc	End Taper	0 to 7 days after taper and	complete. Medication taper for psychoactive medications				
paı		stabilization end; up to 77	should occur prior to Visit 3. Medication taper for medications				
Pre		days after V0	with drug-drug interactions without a psychological concern				
			should occur prior to Visit 5.				
	Preparatory	1.5 hours/	90-minute Preparatory Session. PCL-5, SDS, C-SSRS, and				
	Session 3	As soon as possible post	exploratory measures collected by study team.				
	Baseline	V2 & Medication Taper;					
	PCL-5 T1	1 to 14 days before V4					
	(Visit 3)						

	Treatment Period From Experimental Session 1 (Visit 4) to Integrative Session 3.3 (Visit 15): 6 to 20 weeks						
Study Visit/ Visit #		Visit Duration/ Visit Timing	Brief Description of Events				
	Experimenta 1 Session 1 (Visit 4)	At least 6 hours + overnight/ 1 to 14 days after V3	First Experimental Session occurs 1 to 14 days after Preparatory Session 3 (Visit 3), it lasts at least 6 hours with overnight stay. Dose is 80 mg with supplemental half-dose of 40 mg unless tolerability issues emerge with the first dose or it is refused by the participant. C-SSRS administered pre- and post- Investigational Product administration.				
Treatment 1	Integrative Session 1.1 (Visit 5)	1.5 hours/ Morning after V4	90-minute Integrative Session the morning after Visit 4. Followed by phone check-ins every other day for 14 days. C-SSRS administered during Integrative Session 1.1 and phone calls.				
·	Integrative Session 1.2 (Visit 6)	1.5 hours/ 10 to 18 days after V4; at least 2 days after V5	Between 10 and 18 days after Visit 4, a 90-minute Integrative Session is completed. C-SSRS, PCL-5, and LEC-5 are administered.				
	Integrative Session 1.3 (Visit 7)	1.5 hours/ at least 2 days after V6; 1 to 14 days before V8	90-minute Integrative Session at least 2 days after Integrative Session 1.2 (Visit 6) and 1 to 14 days before Experimental Session 2 (Visit 8). C-SSRS administered.				
	Experimenta 1 Session 2 (Visit 8)	At least 6 hours + overnight/ 21 to 56 days after V4; 1 to 14 days after V7	Second Experimental Session occurs 1 to 14 days after Integrative Session 1.3 (Visit 7), it lasts at least 6 hours with overnight stay. Dose is 80 or 120 mg plus supplemental dose unless tolerability issues emerge with the first dose or it is refused by the participant. C-SSRS administered pre-and post-Investigational Product administration.				
Treatment 2	Integrative Session 2.1 (Visit 9)	1.5 hours/ Morning after V8	90-minute Integrative Session the morning after Visit 8. Followed by phone check-ins every other day for 14 days. C-SSRS administered during Integrative Session 2.1 and phone calls.				
Tre	Integrative Session 2.2 (Visit 10)	1.5 hours/ 10 to 18 days after V8; at least 2 days after V9	Between 10 and 18 days after Visit 8, a 90-minute Integrative Session is completed. C-SSRS, PCL-5, and LEC-5 are administered.				
	Integrative Session 2.3 (Visit 11)	1.5 hours/ at least 2 days after Integrative Session 2.2 (Visit 10) 1 to 14 days before V12	90-minute Integrative Session at least 2 days after Integrative Session 2.2 (Visit 10) and 1 to 14 days before Experimental Session 3 (Visit 12). C-SSRS administered.				
	Experimenta 1 Session 3 (Visit 12)	At least 6 hours + overnight/ 21 to 56 days after V8; 1 to 14 days after V11	Third Experimental Session occurs 1 to 14 days after Integrative Session 2.3 (Visit 11), it lasts at least 6 hours with overnight stay. Dose is 80 or 120 mg plus supplemental dose unless tolerability issues emerge with the first dose or it is refused by the participant. C-SSRS administered pre- and post-Investigational Product administration.				
Treatment 3	Integrative Session 3.1 (Visit 13)	1.5 hours/ Morning after V12	90-minute Integrative Session the morning after Visit 12. Followed by phone check-ins every other day for 14 days. C-SSRS administered during Integrative Session 3.1 and phone calls.				
L	Integrative Session 3.2 (Visit 14)	1.5 hours/ 10 to 18 days after V12; at least 2 days after V13	Between 10 and 18 days after Visit 12, a 90-minute Integrative Session is completed. C-SSRS, PCL-5, and LEC-5 are administered.				
	Integrative Session 3.3 (Visit 15)	1.5 hours/ At least 2 days after V14	90-minute Integrative Session at least 2 days after Integrative Session 3.2 (Visit 14). C-SSRS administered.				

	MAPPUSX Protocol
Amendment 3	Version 1: 15 March 2023

Study Termination From Experimental Session 3 (Visit 12) until Study Termination (Visit 16): 24 to 32 days								
Study Visit/ Visit #		Visit Duration/ Visit Timing	Brief Description of Events					
Primary Outcome Study Termination	Primary Outcome PCL-5 T5 Study Termination (Visit 16)	2 hours/ 24 to 32 days after V12	Primary Outcome PCL-5 and LEC-5 completed. Complete self-reported and safety measures. Create an exit plan for participant. Collect weight and final blood pressure. Invite participant to the extension study for LTFU.					

Table 2: Primary Outcome (PCL-5) Data Collection by Visit

PCL-5 Number	Visit	it Description/Timing	
Initial PCL-5 T0	Screening	Prior to enrollment and initiation of tapering	
Baseline PCL-5 T1	V3	Baseline	
After tapering and stabilization, at Preparat		After tapering and stabilization, at Preparatory Session 3 (Visit 3)	
PCL-5 T2	V6	10 to 18 days after Experimental Session 1	
		At Integrative Session 1.2 (Visit 6)	
PCL-5 T3	V10	10 to 18 days after Experimental Session 2	
At		At Integrative Session 2.2 (Visit 10)	
PCL-5 T4	V14 10 to 18 days after Experimental Session 3		
At Integrative Session 3.2 (Visit 14)		At Integrative Session 3.2 (Visit 14)	
Primary Outcome	V16	24 to 32 days after Experimental Session 3	
PCL-5 T5		At Study Termination (Visit 16)	

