4.2 Planned Duration of Study

Full screening may take 70 days after Informed Consent is obtained during the Informed Consent visit. The Preparatory Period begins at enrollment and can be as brief as 5 days but depending on medication tapering could be as long as necessary to ensure an appropriate medication washout. An appropriate psychoactive medication taper schedule should be defined by the treating physician. The taper will be followed by a washout period of five half-lives of drug or active metabolite (whichever is longer). For non-selective irreversible MAOIs, a 2-week washout period following the taper is required (3 weeks in the case of imipramine and clomipramine, tricyclic antidepressants with MAOI activity). The taper followed by washout should be completed for psychological stabilization prior to Baseline PCL-5 (Visit 3). Medication taper for psychoactive medications should occur prior to Visit 3. Medication taper for medications with drug-drug interactions without a psychiatric concern should occur prior to Visit 4. The Treatment Period will consist of three Experimental Sessions 3 to 8 weeks apart with associated non-drug Integrative Sessions.

Four weeks after the final Experimental Session 3 (Visit 12) and after the final Integrative Session 3.3 (Visit 15), participants will complete Study Termination (Visit 16), including administration of the Primary Outcome PCL-5 assessment.

The minimum time that a participant who completes all study visits from Screening to Study Termination will be in the clinical trial is 13 weeks, and the maximum is dependent on medication tapering. The average participant is expected to complete the study in 22 weeks. Any delays between visits outside of the protocol-defined windows may result in a corresponding extension of study duration and should be documented as a deviation as appropriate.

All participants who complete the study will be asked to participate in a LTFU extension study at least 6 months after the last Experimental Session.

MAPPUSX Protocol

4.3 Interruptions and Accommodations Due to COVID-19 Pandemic or Any Other **Unforeseen Emergency at Clinic Locations**

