7.0 Study Procedures

All assessments must be performed by qualified study staff delegated these duties on the Site Responsibilities Log. The Clinical Research Associate (CRA) should be notified of any delays or deviations to study procedures and Medical Monitor consulted if necessary. If there are delays of more than 7 days between visits or contact, the site should assess the need for additional telephone contact with the participant to ensure safety.

Table 5: Time and Events-Study Procedures

		Screening Period (1 to 6 weeks)		Preparatory Period (At least 5 days, depending on medication tapering)							
		Screening			Prepa	aratory					
Visit	Phone Screening	Screening	IR Screening	V0	V1	V2	V3				
Visit Description	Phone Calls	In-person/Remote Visits & Labs	Telemedicine	Enrollment	Prep. 1	Prep. 2	Prep. 3				
Visit Timing	Prior to Initial Screening	Over 7 to 70 days	After initial screening visit	2 to 14 days post IR Screening	0 to 14 days after V0	At least 2 days after V1 (depending on tapering)	Post V2 & Taper; 1 to 14 days before V4				
Initial Phone Screen	✓										
Informed Consent	Send Copy	✓									
Follow-up Phone Screen	✓										
Assess Eligibility	✓	√	✓	✓	√	✓	✓				
Medical/Psychiatric History	✓ A	✓			✓	✓	✓				
Past/Current Medication &	✓	✓		✓	✓	✓	√				
Adherence											
Weight		✓									
Resting Vitals		✓									
Physical Exam		✓									
ECG & Rhythm Strip		✓									
Clinical Lab Tests		✓									
Drug Screen		✓					✓				
Pregnancy Screen		✓					✓				
Enter Participant in eCRF		✓									
Independent Rater Assessment			✓								
Medication Taper				✓	√	√					
Study Enrollment				✓		_					
All AEs ^B				✓	√	✓	✓				
90-min Preparatory Session					✓	✓	✓				
Phone Call Follow-up ^C						✓					
Measures (ePRO or Clinician- Administered D		√	✓		√	√	√				

A At Screening, collect data on previous hospitalizations and healthcare utilization. Site physician may request participants to obtain medical/psychiatric records generated since the end of the parent study as required for eligibility assessment

B All Adverse Events (AEs) includes collecting Serious Adverse Events, AEs of Special Interest, AEs of Psychiatric Status, AEs requiring medical advice or attention, AEs that indicate withdrawal of a participant, and all other AEs

^C If needed, call participant to confirm medication tapering and stabilization is complete prior to Visit 3 ^D Refer to Table 6: Time and Events-Measures for details

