During one of the Preparatory Sessions, if possible, the therapy pair will introduce the participant to the attendant who will remain with the participant during each overnight stay after each MDMA-assisted therapy session. The attendant will be an individual with previous training in caregiving. The site will make all attempts to have the same attendant for each Experimental Session for a given participant, but it is not guaranteed.

7.2.1 Preparatory Sessions 1 and 2

Preparatory Session 1 (Visit 1) will occur 0 to 14 days after Visit 0. The visit timing should take in to account appropriate times for monitoring medication tapering.

Preparatory Session 2 (Visit 2) will occur 2 to 75 days after Visit 1. The visit timing should take into account appropriate times for monitoring medication tapering.

If tapering is ongoing at Preparatory Session 2 (Visit 2), the site team will schedule a telephone phone call within 7 days of completion of tapering and stabilization. If tapering is complete or not needed, the site team will confirm eligibility and schedule Preparatory Session 3 (Visit 3) as soon as possible.

7.2.2 Preparatory Session 3

Preparatory Session 3 (Visit 3) should take place as soon as possible after medication tapering and stabilization and 1 to 14 days prior to Experimental Session 1 (Visit 4).

The site team will confirm eligibility and ensure that the participant continues to agree to all lifestyle modifications. If any requirements are not met before or during Visit 3, the participant will be considered a Pre-Treatment Early Termination.

For eligible participants, qualified site staff will:

- Perform urine pregnancy test for participants who are able to become pregnant.
- Perform urine drug test.
- Administer Since Last Visit C-SSRS to determine suicidal risk.
- Actively support participant in the completion of Baseline self-reported measures. Completion of measures does not need to be recorded.
 - PCL-5, under the direction of the therapy pair, who will remind them of the index trauma identified in the parent study to which PTSD symptoms should be anchored

- o LEC-5
- o SDS
- o BDI-II
- CPGS
- o EO-5D-5L
- o SRNU
- o EAT-26
- o HPQSF
- Complete the third 90-minute Preparatory Session with the purpose of confirming all enrollment eligibility is met and completing final preparation for the first Experimental Session.
- Remind the participants of lifestyle modifications, including fasting and refraining from using

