7.3.3 Integrative Sessions

After each Experimental Session, three Integrative Sessions will take place. Each session will consist of 90 minutes of therapy. Integrative Sessions should not be less than 48 hours apart. The therapy pair may record the sessions. Integrative Sessions 1.2, 1.3, 2.2, 2.3, 3.2, and 3.3 may be performed via telemedicine.

MAPPUSX Protocol

Amendment 3 Version 1: 15 March 2023

Treatment 1

- Integrative Session 1.1 (Visit 5): morning after Experimental Session 1 (Visit 4).
- Integrative Session 1.2 (Visit 6): 10 to 18 days after Experimental Session 1 (Visit 4). The participant will complete the PCL-5 and LEC-5.
- Integrative Session 1.3 (Visit 7): at least 2 days after Integrative Session 1.2 (Visit 6) and 1 to 14 days in advance of Experimental Session 2 (Visit 8). This visit serves two purposes: to continue integration and to prepare for the next Experimental Session.

Treatment 2

- Integrative Session 2.1 (Visit 9): morning after Experimental Session 2 (Visit 8).
- Integrative Session 2.2 (Visit 10): 10 to 18 days after Experimental Session 2 (Visit 8). The participant will complete the PCL-5 and LEC-5.
- Integrative Session 2.3 (Visit 11): at least 2 days after Integrative Session 2.2 (Visit 10) and 1 to 14 days in advance of Experimental Session 3 (Visit 12). This visit serves two purposes: to continue integration and to prepare for the next Experimental Session.

Treatment 3

- Integrative Session 3.1 (Visit 13): morning after Experimental Session 3 (Visit 12).
- Integrative Session 3.2 (Visit 14): 10 to 18 days after Experimental Session 3 (Visit 12). The participant will complete the PCL-5 and LEC-5.
- Integrative Session 3.3 (Visit 15): at least 2 days after Integrative Session 3.2 (Visit 14).

During Integrative Sessions, the therapy pair will:

- Inquire about any possible changes in health. Assess the participant's mental health and the status of any previously recorded AEs. Record AEs as described in Section 10.0 Safety.
- Inquire about concomitant medication use and adherence.
- Administer Since Last Visit C-SSRS to determine suicidal risk.

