11.0 Concomitant Medications

11.1 Tapering Instructions

The site physician will record concomitant medications during Screening. If the prospective participant is being treated with psychiatric medications at enrollment, the prospective participant will be encouraged to discuss medication tapering with their outside treating physician, if any, and will be required to give the site physician permission to do so as well. Additionally, participants who are taking prohibited opioids will be cross-tapered to an allowable opioid (hydrocodone, morphine, and codeine) under the care of their prescribing physician.

MAPPUSX Protocol

Amendment 3 Version 1: 15 March 2023

The site physician will consult the prescribing physician to initiate medication tapering for participants, as they must refrain from taking psychiatric medications throughout the study, with some exceptions (see Section 11.2 Allowed Concomitant Medications). The prescribing physician's opinion about medication discontinuation will be documented either in writing from the prescribing physician, or in writing by the site physician documenting phone contact with the prescribing physician. Tapering will follow a time course appropriate for the medication based on its half-life or activity, with the Baseline PCL-5 at Preparatory Session 3 (Visit 3) scheduled to occur after complete washout for psychoactive medications and Experimental Session 1 (Visit 4) scheduled to occur after complete washout for medications with drug-drug interactions without a psychological concern (5 half-lives of parent drug or active metabolite, whichever is longer, 2 weeks for MAOIs, and 3 weeks for imipramine and clomipramine).

The therapy pair will request information about any changes in medication at each contact. The site physician will be responsible for reviewing and confirming all medications collected during the study.

All medications, non-prescription and prescription, will be collected from Screening through 7 days after the last Experimental Session. From 7 days after the last Experimental Session through Study Termination, only prescription or non-prescription medications taken to treat AEs will be collected. Throughout the protocol, all medications used to treat AEs will be collected, and all changes including discontinuations or additions to medications will be collected. The study team will also inquire about concomitant medication adherence and document all information on the Concomitant Medications eCRF.

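### Table 1 of the protocol puts the taper deadline for one class of interacting drugs after the first MDMA dosing session; Sections 4.2 and 11.1 put it before

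*Protocol*

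**What the plan says.** The protocol divides medications to be tapered into psychoactive drugs and drugs that interact with MDMA but raise no psychological concern. For psychoactive drugs, Table 1 and Sections 4.2 and 11.1 all place taper or washout before Visit 3. For the second class they differ.

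- **Table 1 (Section 4.1), end-of-taper phone call row:** the taper "should occur prior to Visit 5".
- **Section 4.2:** "Medication taper for medications with drug-drug interactions without a psychiatric concern should occur prior to Visit 4".
- **Section 11.1:** "Experimental Session 1 (Visit 4) scheduled to occur after complete washout for medications with drug-drug interactions without a psychological concern".

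Table 1 describes Visit 5 as a "90-minute Integrative Session the morning after Visit 4", and Section 7.3.3 gives the same timing. Visit 4 is Experimental Session 1.

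Footnote C of Table 5 (Section 7.0) gives a further anchor without naming a medication class: "If needed, call participant to confirm medication tapering and stabilization is complete prior to Visit 3".

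**The concern.** A limit set at Visit 5 falls after dosing at Visit 4. On the Table 1 sentence alone, a drug that the protocol itself describes as interacting could still be under taper when MDMA is given. The sentence is an operational rule: it sits in the row for the call at which staff confirm that the taper is complete.

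Two things are at stake. The first is safety at the first dosing in this study. The second is consistency across sites: the same taper timing would comply with Table 1 and deviate from Section 4.2, so its classification as a deviation would depend on which page was read.

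There may be a further consequence. Section 11.3 withdraws from treatment any participant who uses a drug with MAOI activity, non-psychiatric ones included, between Visit 4 and Visit 16. The documents do not say whether such drugs belong to the Table 1 class. If they do, a taper running on between Visit 4 and Visit 5, which Table 1 permits, would meet that withdrawal criterion.

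**Working it through.** No statistical figure is involved, so the check sets the passages side by side on one time axis, with Visit 4 as day 0.

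| Source | Milestone | Limit | Day |
|---|---|---|---|
| Table 1, end-of-taper call | taper | before Visit 5 | before about day +1 |
| Section 4.2 | taper | before Visit 4 | before day 0 |
| Section 11.1 | complete washout | before Visit 4 | before day 0 |
| Table 5, footnote C (no class named) | taper and stabilization | before Visit 3 | before a visit held on day −14 to −1 |

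The last row uses the window in Table 1 and Section 7.3.1, which puts Visit 4 between 1 and 14 days after Visit 3.

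**Same class?** Table 1 and Section 11.1 speak of a psychological concern, and Section 4.2 of a psychiatric one. Table 1 and Section 4.2 each set Visit 3 for psychoactive drugs and then give a second deadline in nearly the same words. Section 11.1 makes the same split. I read all three as one class.

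**Table 1 against Section 4.2.** Both speak of taper. Gap = (+1) − 0 = about 1 day, or one visit, with the dosing session inside it.

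**Table 1 against Section 11.1.** Section 11.1 requires washout to be complete. With half-life h in days, under its five-half-life rule the taper must end by day −5h. Gap = 1 + 5h days. The documents give no half-lives for this class, so no day count follows.

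**Does other text cure it?**

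- The Medication Taper row of Table 5 is ticked at V0, V1 and V2 only, and the Treatment Period part has no such row. SAP Table 2 matches.
- Table 1 times Visit 3 after "V2 & Medication Taper", and Section 7.2.2 says that Visit 3 "should take place as soon as possible after medication tapering and stabilization". Neither names a class.
- Sections 3.3 and 11.3.1 require a five-half-life hold before each Experimental Session. They exempt listed drugs and any others the research team approves.
- Section 7.3.1 has a medication review and a check of compliance with Section 3.3 before dosing.

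These provisions lower the chance that a taper is unfinished at Visit 4. They leave the two written limits on opposite sides of the dosing session.

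**The case against.** The conflict itself is hard to dispute; the case on the other side is that it matters little.

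- **Section 11.0 governs.** Section 7.1.5 sends sites to Section 11.0 for all taper details, while the Table 1 sentence sits in a column of brief descriptions. This is the strongest point. It shows where a site that noticed the conflict would turn. It does not help a site that read only Table 1.
- **The row's position limits the literal reading.** It lies in the Preparatory Period, which ends at Visit 3, and comes before the Visit 3 row. That is fair as context, but the sentence still names Visit 5.
- **Visit 5 is probably a numbering slip.** Section 7.2 lists a Visit 4 task among those for the Preparatory Sessions, which are Visits 1 to 3, so a number one too high may have occurred elsewhere. This is plausible but unproven, and a slip in a timing rule still needs correcting.
- **Footnote C does not conflict.** A taper finished before Visit 3 is also finished before Visit 4. That is correct as logic. The footnote also names no class, and Section 11.3 likewise ties a general washout rule to Visit 3. It belongs in the reconciliation as an item to check and is not a second error.
- **The washout gap is not an extra error in Table 1.** Section 4.2 also speaks of taper, so it differs from Section 11.1 in the same way. This stands: the firm size is one visit, and taper versus washout is a separate ambiguity.
- **The exceptions to the hold may be irrelevant.** Nothing shows that a drug tapered for an interaction would be exempt. Nothing rules it out either, since the research team may approve others.

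**Conclusion.** The concern holds. Table 1 contradicts Sections 4.2 and 11.1 on when this class must be tapered. The firm size is one visit, about one day, spanning the first MDMA dosing in this study. This rests on reading the psychological and psychiatric wordings as the same class, which the parallel sentences support.

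The practical risk is reduced by the surrounding text and cannot be quantified, because the documents do not state how many participants take such drugs. No effect on the primary outcome is claimed. The documents do not settle whether Visit 5 is a slip or a separate rule, and this review does not say which visit is right. The point should be fixed because the rule bears on safety at dosing and the correction is cheap.

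**What to change.** The sponsor's medical team should decide which visit anchors this medication class and make Table 1, Section 4.2 and Section 11.1 agree. The same pass should check whether Table 5 footnote C is meant to cover this class, use one name for the class throughout, and state whether the limit refers to the end of taper or the end of washout. The choice of visit is a clinical decision for that team.

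The cost is a clarification memo or administrative amendment and a notice to sites. No procedures, visits or data items are added.
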